All participants, clinical staff, and research staff (including those performing outcomes assessments and administering the drug/placebo) will be blinded to the randomization allocation. The investigational pharmacy (which will not be blinded) will prepare the lorcaserin/placebo for administration in similar forms and packaging to prevent unblinding.

If any unexpected, adverse event occurs that may be directly related to the study protocol, unblinding of treatment allocation for that specific participant will occur, as needed, for the principal investigator and IRB (the outcomes assessor(s) would still remain blinded if the patient continued in the trial). Time points and the number of 'unblinding' episodes will be recorded.

4-d) Justification of why participants will not receive routine care or will have current therapy stopped.

All participants, regardless of study group, will continue to receive routine medical care in the ICU. For safety reasons, in consultation with a panel of experts (Drs. [name] – Critical Care; [name] – Clinical Pharmacology; [name] – Psychiatry, [name] – MICU Pharmacist), the following procedures were developed and will be followed in the event a participant is scheduled to receive pharmacologic therapies that may potentially interact with the study drug (see Appendices A and B for list of drugs) to minimize the risk of serotonin syndrome or other potential adverse drug effect from CYP2D6 effect on drug metabolism.

1. First, a non-interacting substitute will be sought in consultation with the primary clinical team.
2. In the event that no safe and effective substitute is available, and the interacting agent is classified in
 - a. Appendix A, participants will be excluded or withdrawn from the study.
 - b. Appendix B participants will not receive more than one other serotonergic agent during the trial, with consideration of the following strategies when/if feasible
 - i. In consultation with the participant's clinical team, a decision will be made regarding the safety of temporarily discontinuing a non-essential drug therapy before the start of the 4-day protocol, and restarting the drug at least 2 days (i.e., 4 half-lives of lorcaserin) after the last administration of lorcaserin/placebo.

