 - ii. If the dosage of any interacting agent (e.g., analgesic) is routinely titrated for desired clinical effect, the clinical team will be informed and cautioned to ensure titration occurs with the consideration for potentiation or decrease in the interacting agent's effect.
 - iii. If neither substitution, temporary discontinuation or titration of a potential interacting agent is possible, the patient will be excluded / withdrawn from the study.

4-e) Justification for inclusion of a placebo or non-treatment group.

In our proposed study, patients will be randomized to receive either lorcaserin or Placebo. The FDA-approved drug under study in this trial, lorcaserin, does not have any published data supporting efficacy for muscle weakness in the ICU. Hence, no therapy known to be effective is being withheld from the placebo group. Given that our primary and secondary outcomes are based on semi-objective assessments of muscle strength or subjective assessments of cognitive/psychological symptoms, a control group (with blinded outcomes assessments) is required to reduce bias in patients' outcome assessment. Patients in the control group will continue with routine therapy as deemed appropriate by the clinical team.

4-f) Definition of treatment failure or participant removal criteria.

1. Participants will be removed from this study if the surrogate decision-maker, the patient (when capable of medical decision-making) or the patients' medical team makes a request for removal from the study.
2. As stated in Section 4-d, in the event a participant is scheduled to receive pharmacologic therapies that may potentially interact with the study drug (see appendix A), and substitution, gradual titration or discontinuation of interacting agent is not safe or feasible, within the decision rules outlined in Section 4-d, the participant will be withdrawn from the study.
3. The study drug or placebo will be discontinued for the following physiologic changes. Data collection will continue in these participants.
 1. An increase AST > 8 times the upper limit of normal (ULN)
 2. An increase in ALT > 8 times ULN,
 3. A decrease in creatinine clearance <30 mL/min,
 4. New-onset Q-T prolongation, defined as
 - QTc>500 msec
 - A >60 msec increase in QTc from baseline
 5. New-onset 2nd or 3rd degree heart block without a permanent pacemaker,
 6. Persistent heart rate <60 bpm
 7. New-onset priapism
 8. Serotonin Toxicity (as determined by Hunter Criteria, as previously described)

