 9. New-onset psychosis
 10. Onset of new symptoms of hallucinations or euphoria (as determined by NPI-C assessment as described above)
4. If the patient is given a sedative medication during this brief period between baseline and follow-up testing, with a change in mental status that prohibits the ability to perform muscle strength testing, no further testing or administration of lorcaserin/placebo will be done in that patient and a new patient would be recruited and consented in place of this patient.

4-g) Description of what happens to participants receiving therapy when study ends or if a participant's participation in the study ends prematurely.

Those who end their participation in this study prematurely will not be given any further lorcaserin/placebo doses. Similarly, lorcaserin/Placebo administration will cease upon the end of the study. Cessation of lorcaserin will not be harmful to the patient. There are no known adverse effects associated with withdrawal of lorcaserin and there is no need for tapering. Thus its absence or cessation will not directly cause any adverse outcomes. Patient care will continue without change after cessation of lorcaserin/placebo.

5) Inclusion/Exclusion Criteria

5-a) Inclusion Criteria:

1. Age \geq 18 years old
2. Sepsis [\geq 2 Systemic Inflammatory Response Syndrome (SIRS) Criteria AND known or suspected infection]
3. Muscle weakness [Medical Research Council sum score $<$ 48/60 or handgrip strength $<$ 11 kg in men and $<$ 7 kg in women]
4. Obey Commands [Score for DeJonghe Awakening Score of \geq 3/5]

5-b) Exclusion Criteria (based on medical record review and discussion with patient/surrogate)

1. Severe renal insufficiency [Creatinine Clearance $<$ 30 mL/min – or receiving dialysis]
2. Acute infectious or auto-immune hepatitis, acute liver failure, or a history of cirrhosis without liver transplant
3. History of psychosis
4. Bradycardia, or 2nd or 3rd degree AV block without pacemaker
5. History of valvular heart disease without valve replacement
6. History of priapism
7. Receiving drugs with serotonergic effects and/or CYP2D6 substrates which cannot be substituted stopped or titrated (as described in section 4d).
8. Receiving Sulfonylurea medication at the time of the study
9. Prior neuromuscular or central nervous system disease, including pre-existing neuropathy
10. Inability to perform study's muscle strength assessments based on patient's baseline status prior to hospital admission

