11. Unable to receive, or unlikely to absorb, study drug (e.g. bowel obstruction, ischemia, or infarction; short gut syndrome)
12. Body mass index $>$ 40
13. Patient not expected to survive $>$ 4 days
14. Pregnancy (based on urine or blood test results based on standard practice in the subject's ICU) or lactation
15. Allergy to lorcaserin or lorcaserin taken in the prior 7 days
16. Enrolled in another interventional drug or physical rehabilitation trial
17. Physician declines for patient to be enrolled
18. Patient or proxy declines consent
19. Unable to reach proxy for consent
20. Non-English speaking

6) Drugs/ Substances/ Devices

6-a) The rationale for choosing the drug and dose or for choosing the device to be used.

It is known that activation of serotonin receptors (5-HT_{2C}) in the spinal cord increases persistent inward sodium current to allow motor neurons to fire repetitively, and lorcaserin, as a selective 5-HT_{2C} agonist was used successfully in rat models (see Background, section 3-d)

The lorcaserin dose that normalizes motor neuron firing in rats is 3 mg/kg. The human dose for weight loss is 10 mg PO twice daily, but doses up to 60 mg were tolerated in clinical trials. Based on rat-to-human allometric scaling of both pharmacokinetic parameters and 5-HT_{2C} receptor sensitivity (EC₅₀), the 3 mg/kg dose in a rat is

Date: 1 August 2016

Principal Investigator: [name] PhD

Application Number: IRB00072940

0.26 mg/kg or 18 mg in a 70 kg adult. Based on doses of lorcaserin that were given to patients prior to FDA approval and rat to human allometric scaling, it appears that treatment of patients with effective doses of lorcaserin is feasible (See Background, section 3-e)

6-b) Justification and safety information if FDA approved drugs will be administered for non-FDA approved indications or if doses or routes of administration or participant populations are changed.

See attached IND Exemption document

6-c) Justification and safety information if non-FDA approved drugs without an IND will be administered.

Not Applicable

7) Study Statistics

7-a) Primary outcome variable.

The primary analysis will compare the mean change in hand grip strength from baseline to post-drug testing across the 30 mg intervention dose vs. control group using a two-sample t-test.

7-b) Secondary outcome variables.

Secondary analyses will include the following:

- 1) replication of the primary analysis for the 10 mg intervention dose vs. control group,

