5) Chart Abstraction: There is a risk of loss of privacy, since we will be collected data on participants.

6) Strength testing: Participants may feel some tiredness or discomfort in the arm and leg muscles

7) Questions: There is a small chance that a participant could become uncomfortable, bored or fatigued in answering our questions.

8-b) Steps taken to minimize the risks.

1) Side effects of drug/placebo

a) Serotonin Syndrome and NMS-like reactions:

Although this syndrome is rare, the theoretical risk of serotonin syndrome and NMS-like reactions will be mitigated by

- i. Monitoring participants for liver and renal failure, which may affect drug levels
- ii. Reviewing medication lists to exclude patients on drugs that may cause serotonin syndrome when administered along with lorcaserin (see Appendix A and section 4-d above).
- iii. Allowing participants to be on no more than 1 serotonergic agent (plus lorcaserin/placebo) during the trial.
- iv. Closely monitoring patients, for toxicity using the NPI-C for mental status changes and Hunter Criteria for Serotonin toxicity.

b) Cardiac valvular and conduction abnormalities:

Patients with a history of valvular heart disease, bradycardia, and 2nd or 3rd degree AV block without pacemaker will be excluded. Participants are unlikely to develop new onset valvular defects given that they will only receive two doses in this trial. Participants will be closely monitored via EKG for bradycardia and new onset 2nd or 3rd degree AV block.

c) Cognitive impairment, Psychiatric Disorders (including euphoria and dissociation) and Depression:

Patients with pre-existing cognitive impairment and psychosis will be excluded. During the trial, patients will be closely monitored using the RASS, CAM-ICU and NPS (Neuropsychiatric screening) instruments.

d) Hypoglycemia: Patients will be excluded if they are receiving a sulfonylurea medication at the time of the study

e) Priapism: this is a theoretical risk will be mitigated by excluding patients with a prior history of priapism, and monitoring during the trial via any noted side effect.

2) Risks of stopping/adjusting other medications: These risks will be assessed on a case-by-case basis, in consultation with the participants' medical team.

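### Serotonergic Appendix A drugs are screened by current or scheduled use only, with no minimum interval between the last dose and Day 1

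*Combined protocol and SAP*

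**What the plan says.** Five places in the protocol screen for interacting drugs, and all five look at the present or the future.

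- Section 5-b, exclusion 7: "Receiving drugs with serotonergic effects and/or CYP2D6 substrates which cannot be substituted stopped or titrated". The item then refers to section 4-d.
- Section 4-d, opening: the procedures "will be followed in the event a participant is scheduled to receive pharmacologic therapies that may potentially interact with the study drug".
- Section 4-f, item 2: for scheduled drugs, citing Appendix A, the participant is withdrawn if "substitution, gradual titration or discontinuation of interacting agent is not safe or feasible". This too is subject to the decision rules of 4-d.
- Section 8-b, item 1a ii: "Reviewing medication lists to exclude patients on drugs that may cause serotonin syndrome when administered along with lorcaserin".
- The Appendix A heading, which ties exclusion to current administration and sends the reader to 4-d for details.

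Section 4-d sets the order of action. "First, a non-interacting substitute will be sought in consultation with the primary clinical team" is step 1, and it applies to both drug lists. Only if there is no safe and effective substitute does step 2a apply: "Appendix A, participants will be excluded or withdrawn from the study". Temporary discontinuation and titration appear under step 2b, the Appendix B branch.

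Two intervals appear nearby. Exclusion 15 reads "Allergy to lorcaserin or lorcaserin taken in the prior 7 days". In the Appendix B branch, step 2b i requires "restarting the drug at least 2 days (i.e., 4 half-lives of lorcaserin) after the last administration of lorcaserin/placebo".

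**The concern.** Appendix A is the stricter tier: without a substitute, its drugs exclude the patient. Yet the screen asks only whether the drug is being given or is planned, not when it was last taken. Two ordinary routes pass it. In one, the clinical team substitutes the agent under 4-d step 1; in the other, the agent was already stopped for clinical reasons. Either can happen the evening before Day 1.

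The question matters most for agents whose effect may outlast dosing. Appendix A itself labels four drugs as irreversible MAO inhibitors, and for these the absence of current administration is a weak test. The list also includes linezolid, an antibiotic, in a trial that requires known or suspected infection.

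Safety is objective 2-1, and section 8-a says that the safety of giving lorcaserin with other serotonergic agents has not been established. Toxicity by the Hunter criteria stops study drug (4-f item 3, no. 8). A lorcaserin patient affected after the 10 mg dose would therefore miss the 30 mg dose on which the primary analysis rests, 1 of 10 in that arm.

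**Working it through.** **Does any visible rule set an interval before Day 1?** The five screens quoted above set none. The daily chart review (4-a-6.1) covers interim history and medications but states no look-back. Step 2b i says only that an Appendix B drug is stopped before the 4-day protocol starts. Its 2 days run after the last study dose and rest on lorcaserin's half-life, so they are not a washout of the other drug.

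**How many entries are affected?** Appendix A has 43 rows. Nine are marked for CYP2D6 only: aripiprazole, atomoxetine, carvedilol, flecainide, mexiletine, S-metoprolol, tamoxifen, thioridazine and timolol. That leaves 43 − 9 = 34 marked for serotonin interaction:

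- 4 labelled irreversible MAO inhibitors: clorgiline (listed use is research), isocarboxazid, selegiline and tranylcypromine;
- 5 plants or supplements: 5-hydroxytryptophan, ginseng, Hypericum perforatum, L-tryptophan and Peganum harmala;
- 34 − 4 − 5 = 25 others, including phenelzine, which is listed as an MAO inhibitor without saying whether it is reversible.

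**The protocol's own intervals.** Input: lorcaserin half-life of about 11 h (4-a-6.11). Fraction left = 0.5^(time / half-life).

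- Restart rule: 4 × 11 = 44 h, leaving 0.5^4 = 6.25%. At the stated 2 days, 48/11 = 4.36 half-lives, leaving 4.9%. The protocol's figure of 4 half-lives is reproduced.
- Exclusion 15: 7 × 24 = 168 h; 168/11 = 15.3 half-lives, leaving 0.0025%.

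**Illustration for a recently stopped Appendix A drug.** Assumptions, none of them from the documents: last dose 12 h before Day 1, first-order elimination, half-life t of 6 to 48 h. The 30 mg dose is taken as 48 h after the 10 mg dose (section 3-f), so 60 h after the last dose of the other drug.

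| Assumed t | Left at 10 mg dose, 0.5^(12/t) | Left at 30 mg dose, 0.5^(60/t) | 4t |
|---|---|---|---|
| 6 h | 25% | 0.1% | 1 day |
| 12 h | 50% | 3.1% | 2 days |
| 24 h | 71% | 18% | 4 days |
| 48 h | 84% | 42% | 8 days |

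The Table 3 footnotes allow Day 3 to fall later, which would lower the third column. For longer assumed half-lives of 72 h and 168 h, 4t is 12 and 28 days. A fixed 7-day look-back covers 4 half-lives only for t up to 168/4 = 42 h. None of this arithmetic bounds the effect of an agent labelled irreversible.

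**The case against.** The case against is substantial in places.

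- *Clinical judgement.* The attending confirms eligibility (4-a), a physician may decline enrolment (exclusion 17), the investigator supervises screening daily, and Hunter and neuropsychiatric checks are daily. These are real safeguards, but none sets an interval. Table 3 lists one Hunter examination per study day, without the pre- and post-dose mark given to RASS and CAM-ICU.
- *Dose sequence.* Day 1 is a single 10 mg dose, and the 30 mg dose comes at least 48 hours later. In the illustration at most 18% remains by then for half-lives up to 24 h. This reduces the overlap at the higher dose but does nothing at the first.
- *Weak comparators.* Exclusion 15 gives no reason for its 7 days. They may protect baseline strength and drug levels from carry-over, so they are no proof of a washout standard for serotonergic drugs. The restart rule concerns lorcaserin's own clearance. Both points stand; the two rules show only that the protocol uses intervals.
- *Appendix B also has no interval before Day 1.* True, but the protocol accepts one concurrent Appendix B serotonergic agent with lorcaserin, so residue from that tier lies within what it tolerates.
- *Unseen sources.* Appendix C and the IND exemption document could not be checked and may state an interval.

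A reader might also infer that staff may simply stop an Appendix A drug, without a substitute, to make a patient eligible. The wording of exclusion 7 and 4-f item 2 invites this, but both defer to 4-d, which lists discontinuation only under Appendix B. That route is not clearly open.

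**Conclusion.** The gap is real, and it is limited to two routes: recent substitution under 4-d step 1, and recent stopping for clinical reasons. In the visible text, the minimum interval before Day 1 is none for all 34 serotonin-marked entries, including the four labelled irreversible. That conclusion rests on the wording alone. The 25% to 84% range rests on assumed half-lives and an assumed 12 h stop time, and it does not measure risk.

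Two stronger conclusions might be drawn and are not supported. The first is that the rules allow the very combination Appendix A forbids. Appendix A bars current administration, whereas what remains here is a declining residue. The protocol also tolerates one concurrent Appendix B agent, and section 8-a reports no known case of serotonin syndrome with lorcaserin. The second is that a washout rule would make a single toxic event attributable. With 10 against 5 patients, one event would be hard to attribute either way.

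The change is worth making because it removes an avoidable overlap at little cost in a trial whose first objective is safety. Confidence is medium, since the frequency is unknown and two cited documents are unseen.

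**What to change.** Add a separate exclusion, so that exclusion 7's qualifier does not cancel it. Suggested wording: *Received an Appendix A drug marked for serotonin interaction within 4 half-lives of that drug before the first dose (7 days for plant or supplement entries; a longer interval, set by the 4-d expert panel, for MAO inhibitors labelled irreversible; phenelzine to be classified by the panel).*

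Add to 4-d step 1: *After substitution of such a drug, Day 1 waits until this interval has passed.*

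The 4-half-life default is a starting point borrowed from the lorcaserin restart rule, and the panel may replace it. Exclusion 7, the nine CYP2D6-only entries and Appendix B can stay as they are.

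No new procedure is needed, because medical records and medication lists are already reviewed. The cost is one exclusion, one sentence and a panel decision on the MAO inhibitors. Staff also need a source for the half-lives, which the documents do not give. The downside is that some patients are delayed or not enrolled in a 15-patient pilot: 1 to 8 days from the last dose at assumed half-lives of 6 to 48 h, and longer for slower or irreversible agents. If Appendix C or the IND exemption document already states an interval, it should be carried into the eligibility criteria.

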Below, we propose a sequential 2-level dose escalation study of the safety, pharmacokinetics (drug concentration over time) and pharmacodynamics (i.e., muscle strength response) of lorcaserin in critically ill patients with muscle weakness. We selected two different one-time doses of the study drug to provide dose-response data over a range of doses deemed safe for the ICU setting. As described above, these doses are anticipated to bracket (i.e., fall above and below) the anticipated effective dose based on preclinical studies and established differences between species. Observations for drug effect on muscle weakness, adverse events, and drug concentration will be made at specified intervals after each dose (as outlined below). The time between doses, 48 hours, was selected to provide time for the anticipated drug concentrations and muscle strength effects to return to baseline before the second, higher dose

4) Study Procedures

4-a) Study design, including the sequence and timing of study procedures (distinguish research procedures from those that are part of routine care).

Potentially eligible participants will be identified through screening of the Johns Hopkins Hospital's medical and surgical ICU census (see section 5 for specific eligibility criteria) and IRB approved medical floors under a HIPAA waiver. We will be engaging the CCDA to develop and provide us a daily report of patients on our IRB approved floors who were screened by a treating provider for sepsis and the results of this sepsis screen. Daily reports would be sent to the SAFE virtual desktop. Members of research team who are on this protocol will then review the charts of these patients who had a positive sepsis screen to determine if they meet other inclusion criteria and do not meet exclusion criteria. Potential eligibility will be confirmed by the research team with the patient's attending physician. A treating provider will obtain permission from the patient or surrogate to approach them for a discussion about possible participation in the study.

4-a-1) Informed Consent

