Informed consent will be sought for completion of the study eligibility screening and for participation in the study via oral and written consent respectively. Some patients may be incapable of providing informed consent. In such cases, informed consent will be obtained from their surrogate decision-maker. Surrogate decision-makers will be identified as the individual who is making decisions on behalf of the patient for clinical care in the ICU. Consent will be obtained in two steps. First, oral consent will be obtained to perform a brief (< 5 minute) in-bed assessment of muscle strength using a standardized protocol to determine eligibility. Only those patients who are weak, defined either by (a) composite muscle strength sum-score, using Medical Research Council (MRC) scale, <48/60, or (b) a handgrip strength of <11 kg in men and <7 kg in women(2), will be offered written informed consent (since demonstrated muscle weakness is an entry criteria). During the written informed consent process details on the intent of the proposed study, its design, the type of information collected, and potential risks and benefits of participation will be discussed. If surrogates were consented because of the patient's incapability, we will monitor the patient for return of capability and once they are capable, acquire consent from them for continuation in the study.

4-a-2) Planned flow of participants through the study

After consent is obtained, a chart review will be performed to ensure patient still meets eligibility and safety criteria (sections 5 and 4-f, respectively).

4-a-3) Randomization

After informed consent is obtained, eligible patients will be randomly assigned in a 2:1 ratio to the intervention (lorcaserin) or control group (placebo) respectively. (Please see Table 3 and section 4-a-6 for detailed study events.) Group assignment will be masked for patients, clinical and research staff administering the lorcaserin/placebo, and assessing outcomes (muscle strength, safety outcomes, or serum sample collection), as discussed under section 4-c.

4-a-4) Measurement of Exposures and Potential Confounders:

Patient exposures and potential confounders will be collected at study enrollment and are outlined in Table 1. Table 2 summarizes ICU-related exposures and possible confounders that will be collected during the study.

Table 1: Patient-related exposures and potential confounders – Baseline status

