‡ Peak concentration serum samples will be collected 2 hours ± 15 minutes or 3 hours ± 15 minutes after drug administration (see section 4-a-6.11 for details) and trough concentration serum samples will be collected 24 hour ± 30 minutes after drug administration (see section 4-a-6.11 for details)

† Days 2 and 4 are consecutive to days 1 and 3 respectively.

‡ Day 3 may or may not be consecutive to day 2 depending on assessor availability.

Safety Measures

4-a-6.1) *Chart Review*: A daily review of participants' medical records for interim medical history and medications will be performed to monitor for any safety issues and ensure that participants continue to meet eligibility and safety criteria (see sections 5 and 4-f respectively).

4-a-6.2) *Laboratory Tests*: As indicated in table 3 above, participants will undergo daily blood draws for the following standard laboratory tests: Heme 8 and CMP. In particular, laboratory tests will be obtained prior to every dose of lorcaserin or placebo to ensure that patients meet eligibility and safety criteria (see sections 5 and 4-f respectively). If the relevant tests have already been done for clinical purposes, they will NOT be repeated for research purposes. As these labs are typically measured, at least daily, in the ICU setting, they may not need to be drawn for research purposes and the pre-existing values will be reviewed for research purposes.

4-a-6.3) *EKG*: Daily EKGs will be obtained to determine if participants develop bradycardia, new-onset QT prolongation (as defined in Section 4.f.3.4 below) or new 2nd or 3rd degree AV block. In particular, this test will be obtained prior to every dose of lorcaserin or placebo to ensure that patients meet eligibility and safety criteria (see sections 5 and 4-f respectively). If this test has already been done for clinical purposes, it will NOT be repeated for research purposes. As this test is commonly done, at least daily, in the ICU setting, it may not need to be done for research purposes and the pre-existing test will be reviewed for research purposes.

Date: 1 August 2016

Principal Investigator: [name] PhD

Application Number: IRB00072940

4-a-6.4) Richmond Agitation Sedation Scale (RASS)(25): is a validated instrument to measure agitation and sedation status in ICU patients. Participants will be screened for their sedation status daily as well as pre- and post-drug or placebo administration as indicated in table 3 above.

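### Exclusion 14 leaves pregnancy testing to the routine of the patient's ICU, but the trial also recruits from medical floors and requires no test of its own, so an unrecognised pregnancy could be missed before dosing

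*Combined protocol and SAP*

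**What the plan says.** All references are to the combined protocol and SAP.

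- **Pregnancy rule.** Section 5-b, item 14 excludes "Pregnancy (based on urine or blood test results based on standard practice in the subject's ICU) or lactation". The heading of that list adds a general basis for every item: "Exclusion Criteria (based on medical record review and discussion with patient/surrogate".
- **Where patients come from.** Section 4-a screens the medical and surgical ICU census and also "IRB approved medical floors under a HIPAA waiver". The floor route is an active one, fed by a "daily report of patients on our IRB approved floors who were screened by a treating provider for sepsis".
- **Who may enter.** Section 5-a asks for age 18 or over, sepsis, weakness and the ability to obey commands. Women are plainly eligible, since the weakness threshold is sex-specific: "a handgrip strength of <11 kg in men and <7 kg in women". An ICU stay, current or past, is not among the inclusion criteria.
- **How eligibility is confirmed.** Section 4-a has the research team confirm potential eligibility with the attending physician. After consent, section 4-a-2 says "a chart review will be performed to ensure patient still meets eligibility and safety criteria", and section 4-a-6.1 repeats chart review daily.
- **Study laboratory tests.** Section 4-a-6.2 says "participants will undergo daily blood draws for the following standard laboratory tests: Heme 8 and CMP" and that "laboratory tests will be obtained prior to every dose of lorcaserin or placebo to ensure that patients meet eligibility and safety criteria". Tests already done clinically are not repeated. Table 3 has no row for a pregnancy test.

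**The concern.** The plan treats pregnancy as a reason not to enrol. For the testing that would show it, the plan points to the habits of one kind of unit and then recruits from another kind as well. It does not say what the ICU habit is, and it says nothing about the floors. The blood tests intended to confirm eligibility before dosing cannot show pregnancy.

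What is at stake is participant safety: exposure of an unrecognised pregnancy to a drug from which the protocol means to exclude pregnant women, at up to two dose levels (10 mg on Day 1 and 30 mg on Day 3). No estimate, test or sample-size figure in section 7 depends on this.

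**Working it through.** No arithmetic applies, because the point uses no effect size, SD, error rate or sample size. The check is whether the provisions, read together, ensure that a pregnancy result exists before the first dose.

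1. **Does item 14 itself require a test?** No. It says which results count, namely those produced by routine practice in an ICU. If routine practice produces no result, item 14 does not call for one.

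2. **Does the unit named cover everyone recruited?** Not on the text. Section 4-a opens a floor route that begins with a positive sepsis screen, not with discharge from an ICU. Section 5-a does not close the gap by requiring an ICU stay. For a floor patient who was never in an ICU, item 14 gives no testing standard.

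3. **Does a study procedure supply the result instead?** No. Section 4-a-6.2 and Table 3 were read line by line: chart review, Heme 8, CMP, EKG, sedation, delirium, neuropsychiatric and serotonin-toxicity assessments, strength tests, drug levels, and EMG with nerve conduction. None of these detects pregnancy. The risk-reduction steps in section 8-b do not mention it either.

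4. **How are comparable exclusions handled?** Renal function (item 1) can be checked on the pre-dose chemistry, and bradycardia and AV block (item 4) on the pre-dose EKG. For both, routine results are used if they exist, and otherwise the study obtains the test (sections 4-a-6.2 and 4-a-6.3). Pregnancy has the first half of that arrangement and not the second.

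5. **What do the remaining checks catch?** Record review, discussion with the patient or surrogate, attending confirmation and the post-consent chart review would find a pregnancy that is charted or disclosed. They cannot find one that nobody knows about in a woman who has not been tested.

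6. **What follows?** The conditions for a missed case are: a woman of childbearing potential, no test result from routine care, and a pregnancy not known to the patient, surrogate or clinical team. If all three hold, the text allows randomisation. Allocation is 2:1 (10 lorcaserin, 5 placebo), so she would have a 10/15 = 2/3 chance of assignment to active drug.

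**The case against.** The strongest reply has four parts.

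- **Other safeguards exist.** The 5-b heading covers item 14, so a reader who infers that the exclusion works only through test results goes too far. This stands, and it narrows the gap to unrecognised or undisclosed pregnancy.
- **Floor patients may be step-down patients.** The objectives concern ICU patients. Table 1 collects APACHE II, defined on the first day in an ICU, Table 2 collects the ICU admission diagnosis, and section 4-d describes care continuing in an ICU. Some floor patients may therefore have an ICU to which item 14 can refer. This also stands, so the documents do not support the inference that the safeguard must fail on the floors. But no criterion requires an earlier ICU stay, and the setting is left inconsistent.
- **Routine care may test everyone, or a test may be specified elsewhere.** The documents do not describe unit practice. The IND exemption document, Appendix C and the consent pages are not in the supplied text, so a requirement placed there cannot be ruled out. Even so, the eligibility wording and the laboratory list should agree with the recruitment setting.
- **Using routine results is the plan's general approach.** That is so, but for laboratory tests and EKG the study obtains the test when routine care has not. Asking the same for pregnancy fits the plan's own approach.

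Two further inferences should be resisted. A woman missed in this way would not necessarily receive lorcaserin, since one third of patients are allocated to placebo. Nor do the documents show that surrogate consent will be common: section 4-a-1 says only that some patients may lack capacity, and section 5-a requires patients to obey commands.

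**Conclusion.** The point holds in a limited form. Item 14 ties testing to ICU routine, recruitment extends beyond ICUs, and nothing in the supplied text makes a pregnancy result a condition of randomisation or dosing. An unrecognised pregnancy in an untested woman could therefore be missed, most clearly in a woman enrolled from a floor, and she may receive study drug.

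The size cannot be given as a number. The documents do not state the share of women of childbearing potential, the share enrolled from floors, or how often either setting tests. A count of women who might depend on the rule would not be a count of missed pregnancies, which would be far fewer. The probability in a trial of 15 is low, the consequence could be serious, and the correction is cheap, so the change should be made. The conclusion assumes that no test is specified in the material not supplied. Sample size, power and analysis are unaffected.

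**What to change.** Make two changes.

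1. **Section 5-b, item 14.** Replace the ICU-only wording with wording that covers every recruiting unit, and require a pregnancy test result from the current admission to be on record before the first dose for women of childbearing potential. This reconciles the criterion with section 4-a.
2. **Section 4-a-6.2.** List the pregnancy test. Where routine care has produced a result, use it. Where it has not, obtain one as an add-on to an existing blood sample or as a urine test. Both options are needed, because a separate pre-dose research blood draw may not take place when clinical results already exist, and the Day 1 drug-level sample is taken after dosing.

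The sentence in section 4-d that places all routine care in the ICU should be brought into line with floor recruitment at the same time.

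The cost is a line or so of text in each place and one inexpensive test in the few women without a result on the chart. No extra visit or staff is needed.

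If testing is already universal in the recruiting units, the change only records current practice.
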